- **REDCap Survey on Design Features:** After the focus group occurs, research partners may be asked to complete a REDCap survey that asks for partner input on design changes for the *Move+* program components. Research partners may be asked to select between two design options for a program component feature that is being considered for revision. Whichever option is preferred by more research partners will be selected for the refined *Move+* program components. Program features that are selected by the majority of research partners will be used in the refined *Move+* program components. If a feature splits users 50/50 then we will make revisions to the design options and re-survey research partners. If research partners continue to be split on a feature, we will not go past 4 iterative cycles of this, and the study team will make final decisions on program features, giving priority to the features that best operationalize Self-Determination Theory.
- **Acceptability of Intervention Measure (AIM):** At the end of the 12-week field trial, research partners will be asked to evaluate each *Move+* component using the AIM⁵¹ with a 1-5 Likert scale (1=Completely Disagree, 5=Completely Agree). The AIM is a 4-item questionnaire that asks research partners about whether the intervention component meets their approval, is appealing, whether they like it, and whether they welcome its use. The AIM demonstrated strong psychometric properties including content validity, discriminant content validity, reliability, structural validity, structural invariance, known-groups validity, and responsiveness to change.
- **Intervention Appropriateness Measure (IAM):** At the end of the 12-week field trial, research partners will be asked to evaluate each *Move+* component using the IAM⁵¹ with a 1-5 Likert scale (1=Completely Disagree, 5=Completely Agree). The IAM is a 4-item questionnaire that asks partners about whether the intervention component seems fitting, suitable, applicable, and/or like a good match. The IAM demonstrated strong psychometric properties including content validity, discriminant content validity, reliability, structural validity, structural invariance, known-groups validity, and responsiveness to change.
- **Feasibility of Intervention Measure (FIM):** At the end of the 12-week field trial, research partners will be asked to evaluate each *Move+* component using the FIM⁵¹ with a 1-5 Likert scale (1=Completely Disagree, 5=Completely Agree). The FIM is a 4-item questionnaire that asks partners about whether the intervention component seems implementable, seems possible, seems doable, and seems easy to use. The FIM demonstrated strong psychometric properties including content validity,

discriminant content validity, reliability, structural validity, structural invariance, known-groups validity, and responsiveness to change.

- **Weekly Survey:** Every week during the 12-week field trial, patient partners will be asked to rate their satisfaction with specific program components that they received using a 1-10 Likert scale (1=Strongly Dislike, 10=Strongly Like), to describe their engagement with the virtual fitness membership and rate the classes they tried, and to provide any input for refinement/improvement.
- **Net Promoter Score (NPS):** At the end of the 12-week field trial, research partners will be asked to evaluate each *Move+* component using the NPS. The NPS is a single question with a 1-10 Likert scale: How likely is it that you would recommend the *Move+* component to a friend or colleague? Respondents are grouped as follows: 1) promoters (score 9-10) are loyal enthusiasts who will keep referring others and fueling growth, 2) passives (score 7-8) are satisfied but unenthusiastic customers who are vulnerable to competitive offerings, and 3) detractors (score 0-6) are unhappy customers who can impede growth with negative word-of-mouth. The final NPS score is calculated as % promoters - % detractors. NPS scores range from -100 to +100, with scores >0 indicating good acceptability.
- **Perceived Characteristics of Intervention Scale (PCIS):** At the end of the 12-week field trial, the RD partner will be asked to complete the PCIS (e.g., completed in both phases 1-2). The PCIS is a 20-item scale that measures trialability, relative advantage, compatibility, complexity, potential for intervention adaptation, etc. The PCIS is a reliable measure of perceived characteristics of interventions, with some preliminary support for its validity.⁵² Participant partners will not be asked to complete this scale.
- **Organizational Readiness for Knowledge Translation (OR4KT) Questionnaire:** At the end of the 12-week field trial, the RD partner will be asked to complete the OR4KT. The OR4KT is a 59-item survey that measures setting-level factors that influence program adoption (organizational climate for change, organizational contextual factors, organizational willingness to adjust to changes, leadership, organizational support, and motivation).⁵³ Subscales are grouped into 6 dimensions: 1) Organizational climate for change (10 items), 2) organizational contextual factors (10 items), 3) Change content (9 items), 4) Leadership (10 items), 5) Organizational support (10 items), and 6) motivation (10 items), followed by 1 open-ended question. The validity and reliability of the OR4KT will be assessed in real-life contexts of implementation of evidence-based changes in healthcare.⁵³ Participant partners will not be asked to complete this scale.
- **Global Physical Activity Questionnaire (GPAQ)**^{69, 70}: At baseline and week 12, patient partners will be asked to complete the GPAQ with showcards. The GPAQ is a 16-item interview-based questionnaire, where a research staff member will ask participants to estimate time spent doing different types of physical activity in a typical week. The research staff member will use showcards to help the participant understand types of activities considered moderate vs. vigorous intensity.
- **Basic Psychological Need Satisfaction and Frustration Scale - Exercise (BPNSFS-E)**⁵⁴: At week 12, patient partners and provider partners will be asked to complete the BPNSFS-E. The BPNSFS-E is a SDT-based questionnaire. It assesses satisfaction vs. frustration with basic psychological needs for autonomy, competence, and relatedness with regards to exercise through 12 items (e.g., “The way I exercise is in agreement with my choices and interests”) and a five-point Likert scale, where 1 = “I don’t agree at all” and 5 = “I completely agree”). This 24-item questionnaire has demonstrated validity⁷¹ and gender invariance.⁷²
- **Behavioral Regulations for Exercise Questionnaire (BREQ-3)**⁵⁵: At baseline and week 12, patient partners will be asked to complete the BREQ-3. The BREQ-3 is SDT-based and provides separate scores for each behavioral regulation for exercise (amotivation, external, introjected, identified, integrated, and intrinsic). There are 24-

items with responses that range from 0="Not true for Me" and 4="Very true for Me." It has demonstrated validity and reliability.^{55, 73}

- **Single Category Implicit Association Test (SC-IAT)**⁵⁶: At baseline and week 12, patient partners will be asked to complete the SC-IAT. The SC-IAT is a computerized, time sorting task, which asks participants to rapidly indicate, whether each presented PA stimulus belongs to one of two attributes (good/bad). The SC-IAT for physical activity has shown satisfactory internal consistency (i.e., reliability of the outcome score of trials within the same test)^{74, 75} Three scores will be calculated: *D-Score*, *DW-Score*, and *IP-Score*.
- **Vividness of Movement Imagery Questionnaire (VMIA-2)**⁷⁶: At baseline and week 12, patient partners will be asked to complete the VMIA-2. The VMIA-2 is a 12-item questionnaire where participants rate each mental image in 3 ways (internal visual imagery, external visual imagery, and kinesthetic imagery) from 1 (perfectly clear and vivid) to 5 (no image at all).
- **Movement Imagery Questionnaire (MIQ-3)**⁷⁷: At baseline and week 12, patient partners will be asked to complete the MIQ-3. The MIQ-3 is a 12-item questionnaire to assess an individual's ability to image four movements using internal visual imagery, external visual imagery, and kinesthetic imagery.
- **Internalization of Weight Bias (WBIS-M)**: At baseline and week 12, patient partners will be asked to complete the WBIS-M. We will measure internalization of weight bias using the Weight Bias Internalization Scale – Modified (WBIS-M)⁵⁷. This scale consists of 11 items and uses a 7-point Likert scale (1=strongly disagree; 7=strongly agree). WBIS-M has demonstrated high internal consistency and strong construct validity. The WBIS-M also demonstrated significant correlations with body image, eating pathology, self-esteem, and symptoms of anxiety and depression, and was associated with these outcomes distinctly from anti-fat attitudes and BMI⁵⁷.
- **Body dissatisfaction**: At baseline and week 12, patient partners will be asked to rate their degree of body dissatisfaction. We will measure this using the Figure Rating Scale (FRS) developed by Stunkard et al⁷⁸. Respondents are asked to choose the image that better represents their actual size. Then, they are asked to choose which image represents their ideal body size. The first is considered a measure of perception of one's body (current body image); the second is understood as an adherence to the ideals of beauty socially shared in the culture to which the respondent belongs (ideal body image). The discrepancy between the two is considered a good measure of body dissatisfaction. Positive scores are indicative of the desire to have a larger body size, while the negative ones are indicative of the desire to be thinner. The FRS has indicated good test-retest reliability and moderate correlations with other measures of body image dissatisfaction, eating disturbance, and overall self-esteem.⁷⁹
- **Identity**: At baseline and week 12, patient partners will be asked to rate their level of agreement for each physical activity identity statement. This will be measured using the Behavior Based Identity Questionnaire, which consists of 4 items.⁸⁰
- **Physical Activity Habit Strength**: At baseline and week 12, patient partners will be asked to rate their level of agreement for each physical activity habit statement. The Self-Report Index of Habit (SRHI) Index Strength involves 12-items that assesses physical activity habit strength and automaticity^{81, 82}.
- **Dietary Intake Assessment**: Dietary energy and fat intake will be assessed with a 3-day dietary record. Participants will be asked to log food intake over 3 days including a weekend day.
- **Environment**: Participants will be asked to report their home address, work address, and any changes in these addresses over the 12-week intervention. Home address and work address will be used to obtain census level data about the area in which they live and work, like access to parks and grocery stores.

- **Medication Review:** We will ask patient partners about the medications they are taking at baseline and week 12.

Justification and Risks: These questionnaires are required to assess the primary outcomes of acceptability and feasibility and other pre-specified outcomes of changes in SDT-based constructs and additional behavioral and psychosocial outcomes. Subjects may find it inconvenient to complete the surveys. There are no known risks associated with these procedures.

Additional, Other Pre-Specified Outcome Measures:

Anthropometric Measures

Description: Body weight will be measured using a digital scale accurate to ± 0.1 kg at baseline and week 12. Height will be measured to the nearest 1 mm with a stadiometer at baseline. Blood pressure will be measured with an automatic sphygmomanometer (average of 2 seated values taken after 5 min rest) at baseline and week 12. Waist circumference will be measured at baseline and week 12 with a tape measure just over the iliac crest.

Justification and Risks: These measures are required to assess our primary study outcomes of change in weight and BMI and there are no risks associated with these procedures.

Patterns of PA and Sedentary Behavior

Description: The activPALv4 (PALTechnologies, Glasgow, Scotland) will be used to estimate time spent in moderate-to-vigorous PA (MVPA), light activity, and sedentary behavior over a 7-day period at baseline and approximately week 12. The activPAL is a small (23.5 x 43 x 5 mm) and light (10 grams) device that uses accelerometer-derived information about thigh position to estimate time spent in different body positions (i.e., sitting/lying, standing and stepping). The device is attached to the anterior thigh and is waterproofed by wrapping in a nitrile sleeve. Thus, it can be worn during bathing and overnight, allowing for 24-hour measurement of wake and sleep behavior. The activPAL was used in [name] K23 DK078913 in 114 participants; the device was well-tolerated with wear time averaging >23 hours/day⁸³. The time-stamped "event" data file from the activPAL software will be used to determine time spent sitting, standing, and stepping per day. Using the activPAL program, the event data file will be converted to a second-by-second file and additional metrics of sedentary behavior (e.g., breaks in sedentary time, average duration of sedentary bouts, sleep time) and time in PA intensity category (sedentary, light and MVPA) will be estimated. The activPAL estimates EE (METs) by 1) assigning MET values to sitting/lying and standing events and 2) estimating METs for stepping events. Many studies have validated the activPAL for use in children, adolescents, and adults and report very high levels of accuracy (99-100%) and no adverse events⁸⁴⁻⁹⁰. Participants will also be asked to log all exercise during the 7-day period they wear the activity monitor.

Justification and Risks: This measure is necessary to obtain an assessment of patterns of free-living physical activity, and sedentary behavior. Subjects may find wearing the monitors inconvenient. Rarely, mild to moderate skin irritation or rash can occur due to the activity monitors. If this occurs, the monitor will be discontinued, and the subject evaluated by the study PI.

3 Minute Step Test (TMST)

Description: A TMST will be obtained as a surrogate measure of cardiorespiratory fitness. In accordance with the YMCA TMST protocol⁵⁸ participants will step on and off a 30.5 cm (12 inch) step 24 times per minute for 3 minutes. They will be aided by an electronic metronome set at 96 beats per minute which they are to match with 96 steps (24 ascent-descent cycles) per minute. At one-minute intervals participants will be told "you are doing well" and the time remaining was indicated. Immediately after completion of the test participants rate their perceived exertion using the Borg (6 to 20) perceived exertion scale. Their cumulative heart rate will be determined by auscultation with a stethoscope during the first minute after test completion.

Justification and Risks: The TMST predicts 50-90% of the variance in fitness as assessed by exercise treadmill V02 max testing and is thus an inexpensive surrogate for cardiorespiratory fitness, an important metabolic outcome measure. The TMST is also recommended by the ADOPT working group as an important predictor of response within weight loss interventional studies. The primary risks associated with the TMST are likely to be fatigue, shortness of breath, or muscle soreness during or after the test. It is expected that when these symptoms occur, they will be minor and brief. During the TMST there is a small risk subjects may experience musculoskeletal injuries. During the TMST there is a small risk subjects may trip or fall. During the TMST is a very small risk subjects will experience cardiovascular symptoms such as chest pain, shortness of breath, dizziness, syncope, or lower extremity claudication. Study staff will monitor the test and the test will be stopped if subjects experience any of these symptoms and subjects will be referred to their PCP or to the emergency room for further evaluation depending on the severity of symptoms. Risks of the TMST will be minimized by ensuring all subjects meet the specific study inclusion/exclusion criteria. Subjects will have previously undergone a medical screening including medical history interview and physical exam, and assessment of blood pressure.

D. Potential Scientific Problems:

Making correct inferences when coding qualitative data: There is a risk of making incorrect inferences when coding the qualitative data. However, we will use an iterative process that involves moving back and forth between raw data and emerging themes multiple times, to ensure that participants' experiences are accurately captured. We use a team-based approach to code the qualitative data.

Compliance with *Move+* Intervention: We recognize adherence to PA will not be perfect and we do not expect it to be. The research question we seek to address is not whether participants will fully adhere to the *Move+* program, but rather whether the *Move+* program components are acceptable and feasible.

F. Data Analysis Plan:

F.1 Quantitative Data Analyses: Descriptive statistics will be performed on scale ratings with aspects of the *Move+* program. Aspects of the *Move+* program with less acceptable ratings will be targeted for refinement. Average scores <0 for the Net Promoter Score®, or <3 on any scale from the PCIS will indicate areas for refinement. Demographic information will be analyzed using descriptive statistics. We will also explore within-person changes in other pre-specified outcome measures from baseline to 12 weeks (e.g., PA, weight, waist circumference, blood pressure, cardiovascular fitness) using a paired samples t-test. Normality assumptions will be evaluated, and transformations used (e.g., square root and log) as appropriate. P-values <0.05 will be considered significant. No interim analysis is planned.

F.2 Qualitative Data Analyses: Qualitative data from each cycle will be transcribed verbatim and analyzed using a rapid qualitative analysis approach and a traditional content analytical approach. The qualitative data software program ATLAS.ti will be used for data organization, management, and analysis. Consistent with established qualitative methodology, analysis of interview data will be a continuous, iterative process, beginning with initial data collection and continuing throughout and beyond the data generation period.⁹¹⁻⁹³ We will use a rapid qualitative analysis to understand themes around specific domains (acceptability, feasibility, areas for improvement)⁹⁴. A rapid qualitative analysis involves the use of a templated summary to summarize each transcript. Once templated summaries are complete, they are further condensed into a matrix to identify key points, potential themes, quality and consistency of data collection, directions for further data collection and analysis. A rapid qualitative analysis is used to obtain a quick understanding of what is in the data. In addition, in order to achieve immersion, transcripts will be read

multiple times using a deductive approach guided by the Practical Robust Implementation and Sustainability Model (PRISM) and RE-AIM (Reach, Effectiveness, Adoption, Implementation, and Maintenance) frameworks^{95, 96}, as well as an inductive, emergent approach in order to emphasize respondent perspectives and deemphasize investigator speculations⁹³. Each transcript will be coded using a team-based approach (by [name] and a trained Professional Research Assistant) within ATLAS.ti®. Initial codes will be established, and any questionable codes will be discussed with the study team. We will look for comments/themes of acceptability and feasibility. The PI will meet with her mentors quarterly to discuss emergent new codes, themes, and patterns.⁹⁷⁻⁹⁹

F.3 Mixed Methods Analyses: We will use an iterative convergent mixed methods design¹⁰⁰ to integrate findings from the survey results with qualitative themes to identify intervention areas for refinement. We will look for parallel constructs/themes, identify differences and similarities, and create a joint display to array the integrated results.^{101, 102} We will incorporate what we learn from Aim 1 to create a *Move+* manual. Our goal is to package *Move+* in a manner that it is 1) acceptable to participants and organizations to and 2) can be feasibly integrated into any existing lifestyle weight management curriculum.

G. Summarize Knowledge to be Gained: Over two-thirds of US adults are afflicted with overweight or obesity. Obesity is a serious and increasing public health problem. Physical activity is a key modifiable behavior, which may help promote weight loss and weight loss maintenance. Despite the benefits of physical activity, the majority of adults with overweight or obesity do not meet physical activity recommendations. Participants in lifestyle interventions typically adhere to behavior change recommendations initially, but this adherence steadily declines over time. Although many factors contribute to poor physical activity adherence, absence of accessible, effective, theory-based programs that account for each person's values, motivation, and preferences remains a major barrier. The proposed study is designed to optimize a theory-based, person-centered physical activity program for adults with overweight or obesity. Developing novel approaches to improve physical activity adherence and promote weight loss and maintenance may potentially benefit many people. Identifying a feasible physical activity support program for adults with overweight or obesity could enhance our ability to treat obesity, as well as reduce the risk of chronic diseases, including cardiovascular disease. Thus, the minimal potential risks to participants are balanced by the expected knowledge to be gained from this study.

H. References:

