Appropriateness Measure (IAM) ⁵¹		x	x	x	x
Likert scale (0-10)	Ratings of satisfaction for intervention component(s) by patients and staff every 3 weeks	x	x	x	x
Feasibility of Intervention Measure (FIM) ⁵¹		x	x	x	x
Perceived Characteristics of Intervention Scale (PCIS) ⁵²	PCIS measures trialability, relative advantage, compatibility, complexity, potential for intervention adaptation, etc.		x	x	x
Organizational Readiness for Knowledge Translation (OR4KT) ⁵³	Setting-level factors that influence program adoption (organization climate, organization context, change content, leadership, organizational support, motivation)		x	x	x
Reach/Recruitment	# of patients screened, proportion of eligible screens who enroll	x		x	
Treatment Adherence	[# sessions attended/# provided], self-reported fitness membership usage	x		x	
Outcome Measure Rates	[# patients who complete measures at each time point/# patients randomized]	x	x	x	x
Retention	[# patients who complete 12-wk intervention/# patients who start the intervention]	x		x	
Fidelity and Adaptations	Direct Observation	Move+ sessions will be recorded, and the study PI will review recordings using an a-priori checklist		x	x
Physical Activity Patterns	Accelerometer	The activPALv4 (PAL) will be worn over 7 days to capture total stepping time, stepping time in MVPA, and sedentary behavior	x	x	x
	Global Physical Activity Questionnaire (GPAQ)	The GPAQ consists of 16 items which ask about the time spent doing different types of physical activity in a typical week	x	x	x
	Exercise and Sleep Log	Participants will be asked to record exercise and sleep over 15 days	x	x	x
SDT-constructs	Basic Psychological Need Satisfaction and Frustration Scale - Exercise (BPNFS-E) ⁵⁴	SDT-based; Assesses satisfaction vs. frustration with basic psychological needs for autonomy, competence, and relatedness with regards to engaging in physical activity (for participants) or teaching the program (for providers)	x	x	x
Explicit PA Motivation	Behavioral Regulations for Exercise Questionnaire ⁵⁵	SDT-based; Provides separate scores for each behavioral regulation for exercise (amotivation, external, introjected, identified, integrated, and intrinsic)	x	x	x
Implicit Attitudes	Single	A computerized, time sorting	x	x	x

Towards PA	Category Implicit Association Test ⁵⁶	task, which asks participants to rapidly indicate, whether each presented PA stimulus belongs to one of two attributes (good/bad)			

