Participants will be asked to sign an eConsent via REDCap or Docusign if they agree to participate in the study. If a participant declines eConsent, they will be given the option to sign a paper consent in-person or remotely and email their signed consent to the study team. Following completion of informed consent procedures, potential participant partners will undergo a health history and physical examination. Health history and physical examinations will be performed by a qualified healthcare provider (Physician Assistant, Nurse Practitioner, or MD) to ensure that they meet study inclusion/exclusion criteria. Body weight and height will be measured to confirm the self-reported BMI. Resting blood pressure and heart rate will be measured. Participants will complete the Physical Activity Readiness Questionnaire (PAR-Q+)¹¹⁴ to screen for any contraindications to exercise. Participants will also complete the Beck Depression Inventory (BDI)⁶² to screen for depression, and the Eating Attitudes Test (EATS-26)⁶³ and the Questionnaire on Eating and Weight Patterns (QWEP-5)⁶⁴ to screen for eating disorders. Any screening results that preclude enrollment will be communicated to potential volunteers who will be recommended to consult with their primary care provider. Participants who meet eligibility criteria will be invited to participate in the study.

Study group assignment: Phase 2 is a single arm, 12-week field trial, thus all participant partners will receive the *Move+* program and there is no inactive control.

C.2 Study Procedures

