Online Fitness Membership	
 Choice in PA type: cardio, strength and conditioning, yoga, meditation Opportunities for social support from other fitness members 	Autonomy, Relatedness	Participants access online
Guided Imagery	
 Weekly 3-5 min recorded sessions Mental images of a positive, fun PA experience⁴⁶ and moving with confidence 	Autonomy, Competence	Trained* RD provides online access to recordings to participants

*Training will ensure RDs provide an autonomy-supportive environment and are confident in teaching PA content

C.2.2 Delivery of Move+ Program: 10 research partners (9 patients, 1 RDN) will complete a single-arm 12-week field trial, where an RDN delivers ≥1 Move+ session per week (group-class, 1:1, and/or guided imagery), remotely. Patients will receive a 12-week online fitness membership, using the option with the highest acceptability from Aim 1 Phase 1 (COMIRB # 22-0147). Research partner recommendations will be used to refine intervention components. Research partners will be compensated for their time in completing the 12-week single-arm field trial and the quantitative and qualitative measures. See Table 3 below for the schedule of delivery of components.

Table 3. Schedule of Delivery of Move+ Program Components

Program Component	Intervention Week												
	0	1	2	3	4	5	6	7	8	9	10	11	12
Introduction to the Study	x												
Group-Based Class		x			x				x				
Individualized Support Session				x			x				x		
Guided Imagery Sessions		x	x	x	x	x	x	x	x	x	x	x	x
Access to Online Fitness Center Membership	x	x	x	x	x	x	x	x	x	x	x	x	x

C.2.3 Physical Activity Prescription:

Participants will receive a recommendation to gradually increase moderate intensity PA to 150 min/week over the initial 12 weeks. This target is consistent with current PA guidelines for overall health^{67, 68}. Participants will be instructed in how to use a relative intensity scale⁶⁷ to achieve the target moderate intensity.

D. Description, Risks and Justification of Procedures and Data Collection Tools:

Screening:

Description: See detailed description in Section C.1 above.

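### The end-of-trial acceptability and feasibility ratings have no planned collection at withdrawal; Table 1's completion denominator and the in-trial satisfaction rating also need correcting

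*Combined protocol and SAP*

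**What the plan says.** **Timing of the ratings.** In Section D, Outcome Questionnaires, the entries for AIM, IAM, FIM and NPS share one opening: "At the end of the 12-week field trial, research partners will be asked to evaluate each" Move+ component. The justification that closes that list says "These questionnaires are required to assess the primary outcomes of acceptability and feasibility", together with the other pre-specified outcomes.

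**How NPS is used.** Section D states "NPS scores range from -100 to +100, with scores >0 indicating good acceptability". F.1 states "Average scores <0 for the Net Promoter Score®, or <3 on any scale from the PCIS will indicate areas for refinement". Beyond that, F.1 plans descriptive statistics for the ratings and does not mention people who leave before week 12.

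**Ratings during the trial.** Section D, Weekly Survey: "Every week during the 12-week field trial, patient partners will be asked to rate their satisfaction with specific program components that they received", on a 1-10 scale, with room for suggestions. Table 1 has a 0-10 satisfaction rating every 3 weeks, given by patients and staff.

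**Denominators.** Table 1 defines Outcome Measure Rates as "patients who complete measures at each time point/# patients randomized". Its Retention row divides by patients who start the intervention, and its Reach row refers to enrolment. C.1 says "Phase 2 is a single arm, 12-week field trial, thus all participant partners will receive the" Move+ program, and C.2.2 says "10 research partners (9 patients, 1 RDN) will complete a single-arm 12-week field trial, where an RDN delivers" the sessions.

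**The concern.** The four instruments carry the quantitative part of the primary outcomes, and their planned time point is the end of the trial. Someone who stops at week 5 has been exposed to parts of Move+ and may have the clearest view of what needs changing. No step in the outcome or analysis sections obtains that person's AIM, IAM, FIM or NPS answers on leaving. If the answers are lost, and if leavers are less satisfied than those who stay, the reported ratings lean favourable. With only 9 patient raters, one or two absent answers can move a component across the plan's own NPS threshold. The results are meant to shape the refined program and a later pilot feasibility trial.

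Two smaller matters bear on the same data. The measure that would show how many people answered has a denominator that does not fit a single-arm trial. The in-trial satisfaction rating, which is the main record of what leavers thought, is described in two ways that do not match.

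**Working it through.** **Inputs from the documents.** 9 patients and 1 dietitian (9 + 1 = 10, as stated). NPS is % promoters minus % detractors. A component is flagged for refinement below 0 and called good above 0.

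**Assumptions.** The documents give no dropout rate, so the numbers of leavers and their answers are illustrative. Section D does not say whether the dietitian's NPS is pooled with the patients'; I use patients only. I also assume that each leaver received the component being rated.

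**NPS.** With P promoters and D detractors among 9 patients, full NPS = 100 × (P − D)/9. If k detractors do not answer, observed NPS = 100 × (P − D + k)/(9 − k).

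| P − D | Full NPS | One detractor missing | Two detractors missing |
|---|---|---|---|
| −2 | −22.2 | −1/8 = −12.5 | 0/7 = 0 |
| −1 | −11.1 | 0/8 = 0 | 1/7 = +14.3 |
| 0 | 0 | 1/8 = +12.5 | 2/7 = +28.6 |
| +1 | +11.1 | 2/8 = +25.0 | 3/7 = +42.9 |
| +2 | +22.2 | 3/8 = +37.5 | 4/7 = +57.1 |

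Over this range, one missing detractor loses the flag only at −11.1, and the observed 0 is neither flagged nor good. Two missing detractors lose it at −22.2 (observed 0) and at −11.1 (observed +14.3, which reads as good).

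**The same case from the observed side.** Seven patients answer: 3 promoters, 2 passives, 2 detractors. Observed NPS = (3 − 2)/7 = +14.3. Adding two leavers:

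- both detractors: (3 − 4)/9 = −11.1
- one detractor, one passive: (3 − 3)/9 = 0
- both passive: (3 − 2)/9 = +11.1
- both promoters: (5 − 2)/9 = +33.3

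The flag is lost only in the first case.

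**AIM, IAM or FIM (1 to 5).** Seven completers average 4.0 and two leavers score x, so the full mean is (28 + 2x)/9. For x = 1, 2, 3, 4 it is 3.33, 3.56, 3.78, 4.00. Leavers who agree with completers change nothing. F.1 sets no threshold for these scales.

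**Completion denominator.** Suppose 9 enrol, 1 never starts and 1 leaves, and neither completes week 12. The rate is 7/9 = 77.8% per enrolled and 7/8 = 87.5% per starter. With no non-starter and one leaver, both are 8/9 = 88.9%.

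**Satisfaction rating, side by side.**

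| | Table 1 | Section D, Weekly Survey |
|---|---|---|
| Frequency | every 3 weeks | weekly |
| Scale | 0-10 | 1-10 |
| Raters | patients and staff | patient partners |

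The documents do not say whether this is one survey or two.

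**The case against.** A reader might infer that the plan restricts the primary ratings to completers. The documents do not support that. Section D says research partners will be asked at the end of the trial and does not exclude those who stopped. Table 1 keeps measure completion separate from retention, which leaves room for someone who stops the program but still answers. Nor does C.2.2 show that dropout was overlooked: its wording is descriptive, Table 1 has a Retention row, and Section D on potential problems expects imperfect adherence.

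A reader might also infer that missing ratings go unreported, or that the wrong denominator makes the completion rate meaningless. Both go too far. Outcome Measure Rates is itself a planned report of missingness. In a trial described throughout as single-arm, randomized is close to a slip for enrolled, and the two candidate denominators differ only if someone enrols and never starts.

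The size can fairly be disputed too. The NPS reversals need assumed leavers who are all detractors. F.1 also targets any aspect with less acceptable ratings, and in-trial ratings, coded comments and the mixed-methods integration all feed refinement. A lost flag would not by itself block a change. An early leaver may also lack a rating for a component: Table 3 first schedules individual support in week 3. Finally, the consent pages were removed, so withdrawal provisions there cannot be seen.

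All of this limits the weight of the point, but it does not supply what is absent. The visible sections contain no step to obtain the four ratings when a person leaves and no instruction on reporting respondents per rating. Several of the other inputs (focus group, comments coded from it, design survey) also come at or after the end of the trial. That leaves the in-trial satisfaction rating as the main record of a leaver's view, and its description is inconsistent.

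**Conclusion.** The point holds as an inexpensive improvement of modest weight. The four instruments that assess the primary outcomes are scheduled at the end of the 12 weeks, and the visible outcome and analysis sections plan no collection at withdrawal. Overstatement of acceptability follows only if leavers do not answer at week 12 and are less satisfied; the documents establish neither. Under those assumptions, two missing detractors among 9 patient raters can make a component that should be flagged read as good, and one can take it to exactly 0. No go/no-go decision depends on this. The denominator in Table 1 is a wording correction. The two descriptions of the satisfaction rating are a real inconsistency that must be reconciled. Confidence is moderate, because the dropout counts are assumed and the consent pages could not be read.

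**What to change.** 1. Send the existing AIM/IAM/FIM/NPS survey when a person withdraws, as an optional request covering the components that person received.
2. In F.1, report those answers beside the week-12 ratings and do not pool them silently, since exposure differs. Give the number of respondents out of those enrolled for each rating.
3. In Table 1, replace randomized with enrolled in Outcome Measure Rates.
4. Reconcile the satisfaction rating in Table 1 with the Weekly Survey in Section D on frequency, scale and raters, or state that they are two surveys.

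The cost is one word in Table 1, one or two sentences in F.1, one clarification of the satisfaction survey, and one extra send of an existing survey. No added participants, visits or instruments are needed. The downside is a small request to people who withdraw and possibly slightly less favourable ratings.
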